# STUDY SYNOPSIS

**Title** Absorption and Safety with Sustained Use of Relizorb™ Evaluation

(ASSURE) Study in Patients With Cystic Fibrosis Receiving Enteral

Feeding

Sponsor Alcresta Pharmaceuticals, Inc., [name],

[name]

**Sponsor** Name Title Phone

Contacts Chief Medical

Officer

Director, Clinical Operations

Investigational Device Background

The Relizorb™ digestive enzyme cartridge is a single-use, point-of-care device that connects in-line with existing enteral pump feed sets and pump extension sets. Relizorb is designed to hydrolyze fats contained in the enteral formulas, mimicking the function of the digestive enzyme lipase that is normally secreted by the pancreas. By hydrolyzing fats from enteral formula, Relizorb allows for the delivery of absorbable fatty acids and monoglycerides for patients who receive enteral nutrition and cannot hydrolyze fats normally.

The active component in Relizorb is the digestive enzyme lipase, which is covalently attached to polymeric beads; the lipase-bead complex is called iLipase™. As the enteral formula passes through Relizorb during a tube feeding, it makes contact with the iLipase and the fat in the formula is hydrolyzed into its absorbable forms (fatty acids and monoglycerides) prior to ingestion. The iLipase remains in the cartridge and is not ingested.

# Indication and Classification

The proposed indication is for use in children and adults to hydrolyze fats in enteral formula.

The lipase used in Relizorb is designated by the US Food and Drug Administration (FDA) as generally recognized as safe (GRAS 000216). The FDA Center for Food Science and Applied Nutrition (CFSAN) cleared iLipase as a Food Contact Substance under the Food Contact Notification process on January 20, 2015 (FCN 1498). RELIZORB was cleared by the FDA Center for Devices and Radiological Health (CDRH) as a Class II low-risk device through a *de novo* application on November 20, 2015 (DEN150001) and is indicated for use in adults to hydrolyze fats in enteral formula.

# Number of Patients

Approximately 35 male and female patients with cystic fibrosis (CF) and exocrine pancreatic insufficiency (EPI) will be enrolled in Protocol 0000498 with the intention of obtaining at least 30 evaluable subjects who complete the study. Subjects must be ≥4 years of age, with no upper age limit. Since the inclusion/exclusion criteria for this study is similar to Protocol 0000497, patients who participated in Protocol 0000497 will be eligible to participate in this study after they have completed participation

Title: Absorption and Safety with Sustained Use of Relizorb™ Evaluation (Assure) Study in Patients With Cystic Fibrosis Receiving Enteral Feeding

in Protocol 0000497.

Sites

Approximately 10 sites in the United States will participate in this study. Sites that are actively enrolling patients for Protocol 0000497 will preferentially participate in this study.

Objective

The overall objective of the study is to assess safety and tolerability and demonstrate improved fat absorption with sustained use of Relizorb in patients with CF who have EPI and are receiving enteral nutrition as part of their total nutritional therapy. In this study, subjects will be receiving a semi-elemental formula containing pre-hydrolyzed protein that has a high content of long chain triglycerides (Impact® Peptide 1.5) and will be using Relizorb during their enteral feeding in place of other therapies currently used to aid in fat digestion and absorption, such as pancreatic enzyme replacement therapy (PERT). Plasma concentration of long-chain polyunsaturated fatty acids (LCPUFAs) such as docosahexaenoic acid (DHA; C:22:6n-3) and eicosapentaenoic acid (EPA; C20:5n-3) will be measured as biomarkers of fat absorption. Tissue accretion of LCPUFAs assessed through measurement of erythrocyte membrane concentrations of LCPUFAs such as DHA and EPA, as well as determination of the profile of fatty acids in plasma will also be evaluated as additional biomarkers of fat absorption. Plasma fat-soluble vitamin and serum protein concentrations will also be measured as indicators of effectiveness. All fatty acid, fat-soluble vitamin, and protein concentrations will be assessed in relation to values obtained at the beginning of the run-in period (Day -7), at baseline (Day 0), and during Relizorb use (Days 30, 60, and 90). Safety and tolerability of sustained use of Relizorb will be assessed during use and compared with gastrointestinal symptoms recorded during the observation phase of the study (Day -14 through Day -7).

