LCTs, are pre-hydrolyzed *ex-vivo* just before ingestion and provided in a form readily available for absorption in individuals who lack pancreatic lipase or the physiological capacity to digest fat.

The objectives of this study are as follows:

- Demonstrate that sustained use of Relizorb in conjunction with enteral tube feeding without concomitant use of PERT results in an increase in fat absorption as evidenced by increased plasma concentrations of LCPUFAs such as DHA and EPA, tissue accretion (RBC) of omega-3 fatty acids such as DHA and EPA, and increased concentrations of fat soluble vitamins;
- Show that serum protein levels are maintained despite withdrawal of PERT use associated with enteral tube feeding with sustained use of Relizorb in conjunction with enteral tube feeding using a semi-elemental formula;
- 3. Demonstrate the safety and tolerability of sustained use of Relizorb in conjunction with enteral tube feeding;
- 4. Explore the potential immunomodulatory effect of increased plasma concentrations of DHA and EPA as evidenced by changes in the omega-6 to omega-3 fatty acid ratio and urinary leukotriene concentrations.

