2.2.2 Efficacy Endpoints

The primary efficacy variable is the composition changes (%) of total DHA plus EPA (omega-3 index) in erythrocyte membranes.

The secondary efficacy endpoints include changes in:

- Erythrocyte membrane composition (%) of total DHA
- Erythrocyte membrane composition (%) of total EPA
- Erythrocyte membrane composition (%) ratio of omega-6 to omega-3 fatty acids
- Plasma concentration of total DHA concentration (μg/mL)
- Plasma concentration of total EPA concentration (µg/mL)
- Plasma concentration of total DHA+EPA concentration (μg/mL)
- Plasma composition (%) ratio of omega-6 to omega-3 fatty acids

The exploratory efficacy endpoints include:

- Plasma concentrations of fat soluble vitamins A, D and E
- Serum protein concentrations (total protein, pre-albumin, albumin, transferrin)
- Marker of inflammation (urinary leukotriene LTE₄)
- Weight gain velocity versus historical comparison
- Standardized Body weight and BMI expressed as age-specific z-score via CDC reference.

Plasma concentrations (µg/mL) of total DHA and total EPA measured by ultra high performance liquid chromatography (UHPLC) will be provided by Total EPA+DHA will be calculated as the sum of the concentrations of total DHA and total EPA. Fatty acid composition (%) in both plasma and erythrocytes is measured by gas chromatographymass spectrometry (GCMS) and is provided by

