6. GENERAL ISSUES FOR STATISTICAL ANALYSIS

6.1 General Statistical Methodology

The primary population for safety is the safety population. For the efficacy analysis, the primary endpoint will be conducted on both the per protocol (PP) and ITT populations. All secondary efficacy analyses will be conducted on the ITT population unless otherwise specified.

Continuous variables will be summarized using descriptive statistics, including number of nonmissing values, mean, standard deviation, median, minimum, and maximum. Qualitative variables will be summarized using the number and proportion of each possible value.

The minimum and maximum will be reported with the same degree of precision (i.e., the same number of decimal places with a maximum of 1 decimal place) as the raw data. Measures of location (mean and median) will be reported to 1 degree of precision (with a maximum of 2 decimal places) more than the raw data and the measure of spread (standard deviation) will be reported to 2 degrees of precision (with a maximum of 3 decimal places) more than the raw data. All efficacy endpoints in section 8.1 will use a maximum of two decimal places.

Categorical (qualitative) variable summaries will include the frequency and percentage of subjects who are in the particular category. The denominator for the percentage calculation will be based upon the total number of subjects in the relevant study population unless otherwise specified.

Assessments done on unscheduled visits will not be summarized but will be listed. If any assessments are repeated on the same day and/or time point, the last non-missing assessment will be summarized and/or analyzed.

Statistical tests will be conducted at the 0.05 significance level using 2-tailed tests, and nominal p-values will be reported. SAS software (SAS, Inc., Cary, NC) will be utilized for statistical analysis (version 9.3).

Subject level information presented in a listing will include subject identification number as well gender, age (examples: F/23, M/37). All listings will be sorted by subject identification numbers.

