8.3 Exploratory Efficacy Endpoints

The values for the following endpoints will be analyzed using the same MMRM comparing baseline to Day 90 on the ITT population as described in Section 8.1.

- Serum protein concentration (total protein, pre-albumin, albumin, transferrin)
- Plasma concentration of fat soluble vitamins (A, D and E)
- Urinary leukotriene E4 (LTE4)

The analysis for plasma concentration of vitamins A, D, and E will also be repeated by age subgroups.

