9.3 Clinical Laboratory Evaluations

Laboratory data for Chemistry, Hematology, Urinalysis, and Blood lipids will include the following analytes:

- Chemistry: alkaline phosphatase, alanine aminotransferase (ALT), aspartate
 aminotransferase (AST), bicarbonate, blood urea nitrogen, calcium, chloride, cholesterol,
 creatinine phosphokinase, creatinine, glucose, lactate dehydrogenase, magnesium,
 phosphorus, potassium, sodium, total and direct bilirubin, uric acid
- Hematology: basophils, eosinophils, hematocrit, hemoglobin, white blood cell count, lymphocytes, monocytes, neutrophils, platelet count, red blood cell count, mean corpuscular hemoglobin, mean corpuscular hemoglobin concentration
- Urinalysis: bilirubin, blood, glucose, ketones, leukocyte esterase, pH, protein, specific gravity, urinary creatinine and uric acid
- **Blood Lipids**: total cholesterol, triglycerides (TG), high-density lipoprotein (HDL) and low-density lipoprotein (LDL)

Laboratory data will be summarized separately for each category by visit for the safety population. Descriptive summaries of actual values and changes from Baseline will be presented by study visit.

Laboratory values will be displayed in the data listings and those that are outside the normal range will be flagged as normal, high or low, along with corresponding normal ranges (if available).

Pregnancy test results will be listed separately.

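### Vitamins A, D and E are analysed only as efficacy means and are in no laboratory safety table, although the treatment formula carries 2.32 times the vitamin A of the run-in formula

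*Protocol*

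**What the plan says.** **Role.** The protocol synopsis (Objective) states: "Plasma fat-soluble vitamin and serum protein concentrations will also be measured as indicators of effectiveness". In protocol 2.3, the first objective lists "increased concentrations of fat soluble vitamins" among the findings that would show greater fat absorption. SAP 2.2.2 places "Plasma concentrations of fat soluble vitamins A, D and E" among the exploratory efficacy endpoints.

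**Analysis.** SAP 8.3 states: "The values for the following endpoints will be analyzed using the same MMRM comparing baseline to Day 90 on the ITT population". The vitamins are on that list, and their analysis is repeated by age subgroup. The only vitamin tables planned in SAP 12.1 are 14.2.1.9a and 14.2.1.9b, both efficacy tables. The only vitamin listings in SAP 12.2 are 16.2.5.5.1 and 16.2.5.5.2, both in the efficacy series.

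**Safety laboratory.** SAP 9.3 opens: "Laboratory data for Chemistry, Hematology, Urinalysis, and Blood lipids will include the following analytes". None of the lists that follow contains a vitamin, and neither does protocol Table 2. Safety tables 14.3.4.1 to 14.3.4.4 cover the same four categories. SAP 9.3 also sets the out-of-range flagging rule for laboratory listings.

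**Sampling and feeding.** Protocol Table 1 schedules vitamins A, D and E at all five visits. Subjects are 4 years or older and keep their usual feeding volume, 500 to 1000 mL. They use Peptamen 1.5 in the 7-day run-in and Impact Peptide 1.5 in the 90-day treatment period. Protocol appendices 11.1 and 11.2 give the vitamin content of each.

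**The concern.** All three vitamins can be too low or too high. The plan looks at them in one way, as a mean whose rise is read as a sign of absorption. It sets no upper limit, reference-range category or shift analysis. The two ways in which a mean can rise, repletion of deficient subjects and movement of normal subjects above range, would look alike in the planned tables.

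An upward shift in vitamin A is also what the design would lead one to expect. The formula changes to one with more vitamin A at the same time as a device intended to improve fat absorption is introduced. The report could then present a vitamin A rise as favourable, and its laboratory safety tables would not show whether any subjects, young children among them, finished above range. Both documents name laboratory findings as a safety endpoint. The data needed are drawn at every visit, but the tabulation that serves that endpoint leaves them out.

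**Working it through.** The plan gives no baseline, standard deviation, target or limit for any vitamin, so there is no vitamin figure of its own to reproduce. Its one design calculation concerns DHA (protocol 7.2, SAP 3.2). It does reproduce: 30 subjects at effect size 0.53, with a two-sided one-sample t-test at 0.05, give power 0.801 against the stated 80%. It says nothing about vitamins and is not used below.

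**1. Formula content per 250 mL (protocol 11.1 and 11.2)**

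- Vitamin A: 1615 IU in the run-in formula and 3750 IU in the treatment formula. 3750 / 1615 = 2.32.
- Vitamin D: 200 IU in both. Ratio 1.00.
- Vitamin E: 11.3 IU in the run-in formula. The row label in 11.2 is lost in the text; read by position and unit, it is 25 IU. On that assumption 25 / 11.3 = 2.21.

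**2. Vitamin A per feeding at the permitted volumes** (content × volume / 250)

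- 500 mL: 1615 × 2 = 3,230 IU and 3750 × 2 = 7,500 IU, a difference of 4,270 IU.
- 1000 mL: 1615 × 4 = 6,460 IU and 3750 × 4 = 15,000 IU, a difference of 8,540 IU.

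**3. What this implies for total intake.** Let x be vitamin A from all other sources on a feeding day. The documents do not give x.

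- 500 mL: the total doubles only if x + 7,500 ≥ 2(x + 3,230), so x ≤ 1,040 IU.
- 1000 mL: the total doubles only if x + 15,000 ≥ 2(x + 6,460), so x ≤ 2,080 IU.
- If x = 5,000 IU (assumed): 12,500 / 8,230 = 1.52 at 500 mL and 20,000 / 11,460 = 1.75 at 1000 mL.
- If x = 10,000 IU (assumed): 17,500 / 13,230 = 1.32 at 500 mL and 25,000 / 16,460 = 1.52 at 1000 mL.

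The 2.32 is therefore a ratio of the two formulas. The ratio of total intakes is lower by an unknown amount. The comparison is also with the run-in formula, not with whatever formula the subject used before it.

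**4. What the mean can show.** In a mean over n subjects, a rise of d in one subject adds d / n whatever the starting value. With the planned 30 subjects this is d / 30, whether the subject went from deficient to normal or from normal to above range. The contrast with baseline in SAP 8.3 is the same in either case.

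**5. Where a value above range would appear**

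- Laboratory safety tables 14.3.4.1 to 14.3.4.4: nowhere, since vitamins are not in the panels.
- Efficacy tables 14.2.1.9a and 14.2.1.9b: within the mean, and possibly as the maximum, which SAP 6.1 includes in continuous summaries. Neither gives a count.
- Listing 16.2.5.5.1: as an individual value. The shells are not in the text available, so whether it is flagged cannot be checked.
- Adverse event tables 14.3.1.1 and 14.3.1.2: only if an investigator reports it. Protocol 6.2 allows abnormal laboratory findings as adverse events but gives no vitamin threshold.

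**The case against.** The strongest reply is that the vitamins are an exploratory absorption marker, not a nutritional outcome. A rise in a subject already in range is still evidence of uptake, and the analysis is neutral in form: "Statistical tests will be conducted at the 0.05 significance level using 2-tailed tests". This stands. It is a reason to keep the mean analysis and not to redefine effectiveness as movement from deficient to normal. It does not answer the safety gap.

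A reader might also infer more than the documents support:

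- *Subjects above range are scored as improved.* They are not. There is no responder rule for vitamins; high values raise a mean, and that is all.
- *Excess is invisible to the safety analysis.* This is too strong. Values are listed, protocol 7.7 covers clinically significant laboratory abnormalities, and a reported event would enter the adverse event tables. What is missing is a systematic count.
- *Vitamin A intake more than doubles.* This is shown only for intake from formula, relative to the run-in formula.
- *The formula change threatens excess of all three vitamins.* Vitamin D content is identical in the two formulas.
- *A given share of subjects will exceed the range.* No baseline distribution, spread or limit is stated, so any such figure would rest wholly on assumed inputs.

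**Conclusion.** The point holds as a gap in safety reporting. Vitamins A, D and E are measured five times and analysed only as exploratory efficacy means. No laboratory safety table shows who is outside the reference range, and a high value reaches a safety summary only through an investigator's adverse event report.

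The size that can be stated is the formula ratio for vitamin A, 2.32, or an extra 4,270 to 8,540 IU per feeding relative to the run-in formula. For vitamin E the ratio is 2.21, assuming that the broken row is vitamin E. For vitamin D the case rests on the missing range summary alone. How many subjects would move above range is not known from the documents, and nothing here shows that any would. The point does not make the efficacy analysis invalid. It means that a favourable mean change could not be read safely without a range table beside it.

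**What to change.** 1. Add vitamins A, D and E to the laboratory data in SAP 9.3.
2. Add one safety table to SAP 12.1, on the safety population. For each vitamin and visit, give the number and percent of subjects below, within and above the laboratory's age-specific reference range, with shift from Day 0 (Visit 1 where Day 0 is missing, consistent with SAP 6.3). State the source of the limits before database lock.
3. Make sure that the vitamin listing carries reference ranges and out-of-range flags.
4. Keep the MMRM mean change in SAP 8.3 as the exploratory absorption marker, and add a sentence that it is to be read alongside the new table. Do not replace it with a responder definition.

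The cost is one table, a few lines in the SAP and a check of one listing. No new samples or visits are needed. The downside is small cells: with about 30 subjects in three categories at each visit, the table will be descriptive only.

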### Efficacy

- Evaluate effect of sustained Relizorb use during enteral feedings on fat absorption through serial measurements of plasma and tissue (erythrocyte membrane) concentrations of physiologically relevant LCPUFAs such as DHA & EPA as well as serial determinations of the plasma fatty acid profile changes as biomarkers of fat absorption
- Evaluate effect of sustained Relizorb use during enteral feedings on plasma fat-soluble vitamin concentrations
- Evaluate effect of sustained Relizorb use on the ratio of omega-6 to omega-3 fatty acids as a potential indicator of immunomodulation
- Evaluate effect of sustained Relizorb use on urinary leukotriene levels
- Evaluate effect of sustained Relizorb use on serum protein levels
- Evaluate effect of sustained Relizorb use on growth

#### Safety

Evaluate the safety and tolerability of sustained use of Relizorb as part

Title: Absorption and Safety with Sustained Use of Relizorb™ Evaluation (Assure) Study in Patients With Cystic Fibrosis Receiving Enteral Feeding

of an enteral feeding regimen.

# **Endpoints**

### Efficacy

- Change over time in plasma concentrations of omega-3 fatty acids such as DHA and EPA
- Change over time in tissue (erythrocyte membrane) fatty acid concentrations such as DHA and EPA
- Change over time in the plasma fatty acid profile
- Change over time in the ratio of omega-6 to omega-3 fatty acids
- Change over time in plasma concentrations of fat soluble vitamins A, D, and E
- Change over time in serum protein concentrations (total protein, prealbumin, albumin, transferrin)
- Change over time in markers of inflammation (urinary leukotrienes)
- Change over time in weight and body mass index (BMI) and weight and BMI z-scores

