### Study Design

Protocol 0000498 is a multicenter open label study to evaluate the effect of sustained Relizorb use during enteral feeding on fat absorption, as well as safety and tolerability of sustained Relizorb use, in patients with CF and EPI who are receiving enteral tube feeding.

At study entry (Day -14), blood and urine will be collected as part of the screening evaluation and to assess baseline plasma and erythrocyte membrane concentrations of LCPUFAs such as DHA and EPA, plasma concentrations of other long chain fatty acids, plasma concentrations of fat-soluble vitamins, serum protein concentrations, and urinary leukotriene concentrations. Body weight, height, and BMI will be recorded, as well as historical quantification of use of PERT with daytime meals and with enteral feeding. During an initial 7 day observation period subjects will receive their usual enteral nutrition regimen. If subjects use PERT with their enteral nutrition, this will continue through the observation period, and PERT use will be recorded. The subject will also record gastrointestinal symptoms during the observation week in a

Title: Absorption and Safety with Sustained Use of Relizorb™ Evaluation (Assure) Study in Patients With Cystic Fibrosis Receiving Enteral Feeding

gastrointestinal symptom diary. During a 7-day run in period Day -7 to Day -1), subjects will use a standard enteral formula that contains a prehydrolyzed protein (Peptamen® 1.5) at their normal volume of administration from 500 mL up to a maximum volume of 1000 mL per feeding. If subjects use PERT with their enteral nutrition, this will continue through the run in period, and PERT use will be recorded. Throughout the study, individualized patient standard use of PERT with daily meals and snacks will continue.

Following the run in period, subjects will receive an enteral formula similar to Peptamen 1.5 that has a higher long chain triglyceride to medium chain triglyceride ratio (Impact® Peptide 1.5) at their normal volume of administration from 500 mL up to a maximum volume of 1000 mL per feeding using Relizorb in line for the 90 day treatment period.

During the 90-day treatment period, individualized patient standard use of oral PERT is allowed with daily meals, but use of therapeutic agents currently used to aid in fat absorption, such as PERT, will not be used with Relizorb during enteral feedings.

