- e. Clinical chemistry includes albumin, alkaline phosphatase, alanine aminotransferase (ALT), aspartate aminotransferase (AST), bicarbonate, blood urea nitrogen, calcium, chloride, cholesterol, creatine phosphokinase, creatinine, glucose, lactate dehydrogenase, magnesium, phosphorus, potassium, prealbumin, sodium, total and direct bilirubin, total protein, uric acid and A1C levels.
- f. Urinalysis to include bilirubin, blood, glucose, ketones, leukocyte esterase, pH, protein, specific gravity, urinary creatinine and uric acid.
- g. Blood lipids will include total cholesterol, triglycerides (TG), high-density lipoprotein (HDL) and low-density lipoprotein (LDL).
- h. Serum proteins include total protein, prealbumin, albumin, and transferrin.
- i. A serum Beta-Human Chorionic Gonadotropin (β-hCG) pregnancy test will be performed only for females of childbearing potential. Results must be available prior to Day 1.
- j. Blood samples will be obtained for plasma and red blood cell fatty acid analysis.
- k. Blood samples will be collected to measure levels of Vitamins A, D, and E.
- I. Peptamen 1.5 will be administered as the enteral formula during the run in phase from Day -7 through Day -1.

Alcresta Pharmaceuticals, Inc.
Document Status: Approved/Effective

Title: Absorption and Safety with Sustained Use of Relizorb™ Evaluation (Assure) Study in Patients With Cystic Fibrosis Receiving Enteral Feeding

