## 7.8 Efficacy Analysis

The measurement of the absorption of fats is an important efficacy endpoint, using absorption of fatty acids as surrogate biomarkers for fat absorption. LCPUFA plasma concentrations such as DHA and EPA will be an outcome variable, along with tissue accretion of LCPUFAs, measured as relative levels in erythrocyte membrane, and the profile of fatty acids in plasma. The fatty acid profile will also be used to calculate the ratio of omega-6 to omega-3 fatty acids, another outcome variable. Fat-soluble vitamin (A, D, and E) concentration is an additional efficacy endpoint and will be used as a laboratory outcome variable. Serum protein (total protein, prealbumin, albumin, and transferrin) concentrations and urinary leukotriene concentrations are additional endpoints and also represent laboratory outcome variables.

For all laboratory outcome variables, mean values from samples obtained on Day -14 and Day 0 will be compared using a two-sided test for comparison. The mean value from samples obtained on Day 0 will be used as the baseline for comparison with mean values from samples obtained on Days 30, 60, and 90 using ANOVA.

Body weight, height, and BMI are endpoints and clinical outcome variables. Absolute change in body weight from Day 0 through Days 30, 60, and 90 will be analyzed using ANOVA. To evaluate the effect of Relizorb use on weight and BMI, up to 4 weight and BMI recordings obtained from the medical record at 3 month intervals over the previous 12 months. The historical weight recordings will be used to calculate historical weight gain velocity, expressed as grams of body weight per kilogram of body weight per day. The study weight gain velocity will be similarly calculated by using the body weight values obtained on Days 0, 30, 60, and 90. The historical weight gain velocity will be compared to the study weight gain velocity using a two-sided test for comparison. In addition, the historical weight and BMI recordings, along with the weight and BMI values recorded on Day 0, will be used to calculate a standard score for weight and BMI values recorded on Days 30, 60, and 90.

Title: Absorption and Safety with Sustained Use of Relizorb™ Evaluation (Assure) Study in Patients With Cystic Fibrosis Receiving Enteral Feeding

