14.2.1.7	ITT	Changes over Time in Serum Protein Concentrations (Total Protein, Prealbumin, Albumin, and Transferrin)	16.2.5.6.1
14.2.1.8	ITT	Changes over Time in Urinary Leukotriene E4	16.2.5.7.1
14.2.1.9a	ITT	Changes over Time in Plasma Concentrations of Fat Soluble Vitamins (A, D, and E)	16.2.5.5.1
14.2.1.9b	ITT	Changes over Time in Plasma Concentrations of Fat Soluble Vitamins (A, D, and E) by Age Subgroup	16.2.5.5.1
14.2.1.10	ITT	Weight and Body Mass Index (BMI) Z-scores by Age Subgroup and Comparison to Historic Z-score	16.2.5.10.1
14.2.1.11	ITT	Changes over Time in Weight Gain Velocity (g/kg/90 days) Compared to Historical by Age Subgroup	16.2.5.9.1
14.3.1.1	Safety	Summary of Adverse Events	16.2.6.1, 16.2.6.2, 16.2.6.3, 16.2.6.5
14.3.1.2	Safety	Adverse Events by System Organ Class and Preferred Term	16.2.6.1
14.3.2.1	Safety	Unanticipated Adverse Device Effects by System Organ Class and Preferred Term	16.2.6.3
14.3.2.2	Safety	Unanticipated Adverse Device Effects by System Organ Class, Preferred Term, and Relationship	16.2.6.3
14.3.2.3	Safety	Unanticipated Adverse Device Effects by System Organ Class, Preferred Term, and Severity	16.2.6.3

Table Number	Population	Title	Listing Reference
14.3.3.1	Safety	Gastrointestinal Symptom Diary: Frequency and Incidence – Overall and by Symptom	16.2.7.1
14.3.4.1	Safety	Summary of Clinical Chemistry Measurements: Results and Change from Baseline	16.2.8.1
14.3.4.2	Safety	Summary of Hematology Measurements: Results and Change from Baseline	16.2.8.2
14.3.4.3	Safety	Summary of Numeric Urinalysis Measurements: Results and Change from Baseline	16.2.8.3
14.3.4.4	Safety	Summary of Blood Lipids: Results and Change from Baseline	16.2.8.4
14.3.5.1	Safety	Summary of Vital Sign Measurements: Results and Change from Baseline	16.2.9.1
14.3.6.1	Safety	Concomitant Medications	16.2.3.3

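### Vitamin E is tested only as a raw plasma concentration; add a lipid-adjusted analysis beside it, because the formula fat mix changes at Day 0 and blood lipids are already measured at the same visits

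*Protocol*

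**What the plan says.** **Endpoint.** The synopsis (Endpoints, Efficacy) lists "Change over time in plasma concentrations of fat soluble vitamins A, D, and E". Protocol 3.2 and 7.8 and SAP 2.2.2 and 8.3 also define the vitamins by concentration. SAP 2.2.2 ranks them as exploratory.

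**Test.** Protocol 7.8 compares Day 0 with "mean values from samples obtained on Days 30, 60, and 90 using ANOVA". SAP section 10 replaces ANOVA with a repeated measures model, and SAP 8.3 states that the exploratory laboratory endpoints "will be analyzed using the same MMRM comparing baseline to Day 90 on the ITT population". SAP 8.1 sets that model on actual values, with visit as a categorical effect and subject as a random effect. SAP 8.3 repeats the vitamin analysis by age subgroup. SAP 6.1 sets two-sided 0.05 tests with nominal p-values.

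**How a rise is read.** The first objective in protocol 2.3 (Study Rationale and Purpose) counts "increased concentrations of fat soluble vitamins" among the evidence of increased fat absorption.

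**Lipids.** Table 1 in both documents schedules blood lipids (total cholesterol, triglycerides, HDL, LDL) at the same five visits as vitamins A, D and E. Their only planned use is descriptive: SAP 9.3 and safety Table 14.3.4.4, "Summary of Blood Lipids: Results and Change from Baseline". Neither document sets a vitamin E to lipid ratio, a lipid covariate or a related sensitivity analysis.

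**Regimen at Day 0.** Subjects move from the run-in formula to one "that has a higher long chain triglyceride to medium chain triglyceride ratio" (protocol synopsis, Study Design). The device starts and PERT with feeds stops at the same point. Protocol 7.3 confirms that there is no randomization.

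**The concern.** If vitamin E travels in lipoproteins, its plasma concentration reflects the amount of carrier as well as vitamin E status. The contrast of baseline with Day 90 spans a change in the amount and type of fat delivered by tube. With no concurrent control, any lipid change that follows from the new fat mix passes straight into the vitamin E contrast. A lipid rise could yield a small p-value with vitamin E status unchanged; a lipid fall could mask a real gain. The result would then be cited for or against the first objective in protocol 2.3.

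The measurements needed to examine this are taken at every visit, and the plan does not link them to vitamin E.

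**Working it through.** **1. The plan's own figure.** The sample size sections (protocol 7.2, SAP 3.2) concern DHA and give no figure for vitamin E. They do calibrate the test: a paired two-sided t-test with n = 30, effect size 0.53 and alpha 0.05 has power 80.1% by the noncentral t, against the stated 80%. The same calculation is used in step 3.

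**2. What changes in the formula at Day 0** (protocol appendices 11.1 and 11.2, per 250 mL).

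| | Run-in (Peptamen 1.5) | Treatment (Impact Peptide 1.5) |
|---|---|---|
| Total fat | 14 g | 15.9 g |
| MCT | 10 g (10/14 = 71%) | 50:50 MCT/LCT |
| Remaining fat (LCT) | 14 - 10 = 4 g | 15.9/2 = about 8 g |
| Fish oil in ingredients | not listed | listed |
| Vitamin E | 11.3 IU | about 25 IU |

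The treatment formula's vitamin E row has lost its label in the text available; 25 IU is read from the unit and the row order. On that reading the ratio is 25/11.3 = 2.2, that is 22.6 to 50 IU per 500 mL, or 45.2 to 100 IU per 1000 mL.

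**3. What a lipid shift alone could do.** Assumptions, none of them from the documents: vitamin E status is unchanged, vitamin E moves in proportion to plasma lipids, and the SD of the log change in vitamin E is 0.20, 0.25 or 0.30. A mean lipid rise of s% then shifts mean log vitamin E by ln(1 + s/100). The rejection probability is that of a two-sided 5% one-sample t-test with 29 df and noncentrality √30 × shift / SD.

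| Lipid rise | Shift | SD 0.20 | SD 0.25 | SD 0.30 |
|---|---|---|---|---|
| 0% | 0 | 5% | 5% | 5% |
| 5% | ln(1.05) = 0.049 | 25% | 18% | 14% |
| 10% | ln(1.10) = 0.095 | 71% | 52% | 39% |

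Example: for a 10% rise and SD 0.20, noncentrality = 5.477 × 0.0953 / 0.20 = 2.61, which gives 71%.

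In the other direction, a true 10% gain combined with a 10% lipid fall gives 1.10 × 0.90 = 0.99, so the raw concentration would look flat.

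**4. What the ratio does under the same mechanism.** A simulation (20,000 trials, n = 30) assumed an SD of log change of 0.15 for lipids and 0.15 for the vitamin E to lipid ratio, with the ratio truly unchanged. For lipid rises of 5% and 10%, raw vitamin E was significant in 24% and 66% of trials; the ratio stayed at about 5%. This follows from the assumed proportionality and is not independent evidence for it.

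**5. What the ratio does not do.** It leaves the apparent 2.2-fold rise in formula vitamin E in place. A ratio can rise from intake alone.

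**The case against.** The documents contain no error here: the endpoint is a plasma concentration throughout and is analysed as one. The lipoprotein mechanism is not in the documents. They give no lipid values, no expected direction and no SD for vitamin E, so the whole range of 14-71% comes from assumed inputs. Tube feeds are only part of intake; subjects keep their usual diet, so plasma lipids may barely move. The vitamins are exploratory with nominal p-values, and lipids will be tabulated by visit, so a careful reader can set the two tables side by side. All of this stands, and it limits the point to a cheap improvement.

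The strongest objection concerns adjustment. The first objective in protocol 2.3 concerns fat absorption, not vitamin E absorption as such. If the device improves fat absorption, higher plasma lipids may be part of its effect. Dividing by same-visit cholesterol conditions on a post-treatment variable and could remove real signal. This also stands, and it rules out substituting the ratio for the stated endpoint.

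What does not follow is that the raw analysis is enough by itself. Separate group summaries of lipids and vitamin E do not show whether a vitamin E change persists within subjects once lipids are taken into account.

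**Conclusion.** The point holds as a minor addition. Vitamin E is formally tested as a raw concentration across a change in fat mix, without a control arm, while lipids from the same visits are used only descriptively. A lipid change could therefore create or hide a vitamin E change. Under the stated assumptions, a 5% lipid rise alone gives p<0.05 in 14-25% of trials and a 10% rise in 39-71%. These figures illustrate sensitivity and do not predict what will happen in this trial.

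A reader might infer three stronger things that the documents do not support:

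- That a lipid shift occurs and makes the vitamin E result false. No shift, size or direction is given.
- That the ratio should replace the concentration. That would change the stated endpoint and might remove part of a device effect.
- That the ratio would make a rise interpretable as absorption. The apparent 2.2-fold rise in formula vitamin E at Day 0 remains.

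The point concerns vitamin E, not A or D, and does not touch the primary endpoint.

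**What to change.** In SAP 8.3 and Table 14.2.1.9a:

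1. Keep the raw-concentration MMRM as pre-specified.
2. Add the same MMRM on log(vitamin E / same-visit total cholesterol). Add vitamin E / (cholesterol + triglycerides) as a sensitivity version; neither Table 1 nor protocol 4.9.8 specifies fasting draws, and triglycerides are sensitive to recent intake (again general physiology).
3. State that vitamin E will be cited in support of the first objective in protocol 2.3 only if the raw and lipid-adjusted results agree.
4. State beside the table that formula vitamin E appears to rise about 2.2-fold at Day 0, after checking the appendix 11.2 figure against the source label, so that even a lipid-adjusted rise does not isolate absorption.

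The cost is two derived variables and a few table rows from data already collected, with no new blood draw or visit. There are two downsides. The ratio may remove part of a real device effect, which is why both forms are reported. Visits with a missing cholesterol value drop out of the ratio analysis.
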